## **10) Provisions to Monitor the Data to Ensure the Safety of Subjects\***

Study Staff will maintain the data on paper Case Report Forms and in an electronic database stored in a secure location and on a password-protected computer system. The consent forms will be kept in files which will be stored in a secure location within Jackson Health System. De-identified data will be uploaded to the electronic database. The PI and/or a member of the study team will confirm the completeness of data being entered in the electronic database

In order to protect all subjects' confidentiality, we will store data on a password-protected network. Subjects will receive a study-specific unique identifier and the medical record number (MRN) will be uncoupled from the data. The decoder key for study identifier and MRN will be stored in a separate, password-protected file.

### **Trial Monitoring, Auditing, and Inspecting**

The investigator will permit trial-related monitoring, quality audits, and inspections by, government regulatory authorities, of all trial-related documents (e.g., source documents, regulatory documents, data collection instruments, case report forms). The investigator will ensure the capability for inspections of applicable trial-related facilities. The investigator will ensure that the trial monitor or any other compliance or QA reviewer is given access to all trial-related documents and trial-related facilities.

Participation as an investigator in this trial implies the acceptance of potential inspection by government regulatory authorities.

In addition to the Clinical Monitoring component of this protocol, Quality Assurance (QA) to assess compliance with GCP and applicable regulatory requirements. Data or documentation audited shall be assessed for compliance to the protocol, accuracy in relation to source documents and compliance to applicable regulations.

### **Adverse Event (AE) Definition**

An AE is defined as any untoward medical occurrence in a subject or clinical investigation subject administered a pharmaceutical/medicinal product. An AE does not necessarily have to have a causal relationship with this treatment.

An AE can therefore be any unfavorable and unintended sign (including a clinically significant abnormal laboratory finding, for example), symptom, or disease temporarily associated with the use of a medicinal product (investigational or marketed), whether or not considered related to treatment with the medicinal product.

#### **An AE includes:**

- An exacerbation of a pre-existing illness, sign, symptom, or clinically significant (as determined by the investigator) laboratory test abnormality
- An illness, sign, symptom, or clinically significant laboratory abnormality that is detected or diagnosed after study drug administration
- Pretreatment or post-treatment events that occur as a result of protocol-mandated procedures

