**4) Number of Subjects\***

The study population will be comprised of 75 patients assigned to one of three groups of 25 COVID (+) patients each.

The proportion of subjects with AT3 levels < 100% will be 50/50 randomization of which 25 subjects with AT3 <100% will be standard of care and 25 subjects with AT3<100% will be standard of care with exogenous AT3 supplementation. The third group will be subjects with AT3 levels  $\geq 100\%$ .

- a. 25 patients with endogenous AT3 >100% who receive standard of care only or
- b. 25 patients with endogenous AT3 <100% who receive standard of care only or
- c. 25 patients with endogenous AT3 <100% who receive standard of care plus supplemental AT3.

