**8) Procedures Involved\***

Any member of the study team will discuss potential subjects with the clinical team for appropriate pursuit of informed consent and screening for eligibility.

75 eligible subjects, after consent, will have laboratory blood tests for further screening.

25 of those subjects with endogenous **AT3  $\geq$  100%** will continue with SOC.

50 of those subjects with endogenous **AT3 < 100%** will be will be randomly assigned to begin **SOC plus treatment with exogenous AT3 supplementation or only SOC** treatment. The randomization schedule will be established by a member of the study team that is not involved in the informed consent process.

They will all be followed up for laboratory blood tests, study endpoints and adverse events. If they do not meet entry criteria they will be excluded from the study.

[figure not shown]
Consented subjects will be scored according to The International Society of Thrombosis and Haemostasis Disseminated Intravascular Coagulation scale (ISTH DIC) on study visit days 1, 3, 5, 7, 9 and 11.

The SOFA score will be performed only when the parameter is obtained clinically and monitored for changes in patient status on study visit days 1, 3, 5, 7, 9 and 11. Each organ system is assigned a point value from 0 (normal) to 4 (high degree of dysfunction/failure). It will be calculated on admission and Day 11 using the worst parameters measured during the study visit day. If a parameter is not obtained clinically it will be voided for research purposes.

UM IRB# 20201048

AT3 in COVID-19  
January 24, 2022, Version 6.2

After enrollment and each 48h period (+/- 12 hours) thereafter, blood samples are collected and assayed for routine clinical coagulation and inflammation markers, including AT3 activity, D-Dimer, anti-Xa, fibrinogen, and prothrombin time until Day 11.

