### **Procedures for Reporting Adverse Events**

Adverse events may be spontaneously reported, obtained through non-leading questioning, or noted during examination of a subject. Adverse events will be recorded from the signing of informed consent through the last dose of study drug. Serious adverse events will be recorded from the signing of informed consent through hospital discharge.

At each visit, new AEs are recorded sequentially on the **Adverse Event log**. The AE term will note the diagnosis whenever possible, not the individual signs or symptoms (e.g., myocardial infarction will be recorded rather than chest pain, elevated cardiac enzymes, and abnormal ECT). Also recorded are:

- Start and stop date and time
- Whether or not the event is continuing
- Severity (mild, moderate, severe)
  - Mild: usually transient, requiring no special treatment and generally not interfering with usual daily activities
  - Moderate: usually ameliorated by simple therapeutic maneuvers and impairs usual activities
  - Severe: requires vigorous therapeutic intervention and interrupts usual activities. Hospitalization may or may not be required.

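### The new-onset adverse-event rule and the end of the non-serious adverse-event window are tied to study drug, which 50 of 75 patients never receive

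*Combined protocol and SAP*

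**What the plan says.** **Groups.** Section 4 gives the size: "The study population will be comprised of 75 patients assigned to one of three groups of 25 COVID (+) patients each". Two of the groups get no study drug: "25 patients with endogenous AT3 >100% who receive standard of care only or" and "25 patients with endogenous AT3 <100% who receive standard of care only or". The second of these is the randomised control arm. The third group is "25 patients with endogenous AT3 <100% who receive standard of care plus supplemental AT3".

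**Definition.** Section 10 defines an adverse event as an untoward occurrence in a "subject or clinical investigation subject administered a pharmaceutical/medicinal product", and then mentions products both investigational and marketed. The list headed as what an adverse event includes has three entries: worsening of a pre-existing condition; "An illness, sign, symptom, or clinically significant laboratory abnormality that is detected or diagnosed after study drug administration"; and events before or after treatment that result from protocol procedures.

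**Who is followed, and when.** Section 8 says of all groups: "They will all be followed up for laboratory blood tests, study endpoints and adverse events". Section 10 sets the window: "Adverse events will be recorded from the signing of informed consent through the last dose of study drug". Serious events are recorded from consent to hospital discharge. The Appendix B flowsheet marks adverse events at every visit without restriction by arm, and its note 2 limits capture after the last dose to serious events.

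**The concern.** An adverse-event comparison is only as good as the symmetry of its recording rules. Here one rule about what counts, and one about when non-serious recording stops, refer to an event that happens in only one of the three groups. A coordinator with a standard-of-care patient who develops a new arrhythmia finds no list entry that fits. The same arrhythmia in an infused patient fits the second entry exactly.

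The trial is open label, so the person deciding what to log knows who received AT3. The randomised controls are the comparison that separates effects of AT3 from COVID-19 illness. If their new-onset non-serious events are logged less fully, the AT3 arm can show an excess that owes nothing to the drug, and a real excess is harder to recognise.

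**Working it through.** **1. Counts (Section 4).** 25 + 25 + 25 = 75, which reproduces the stated total. Never given study drug: 25 (AT3 at or above 100%) + 25 (randomised controls) = 50, and 50/75 = 66.7%. Within the randomised comparison: 25/50 = 50%.

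**2. The rules applied to an undosed patient.**

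| Provision | Tied to study drug? | Usable in an undosed patient? |
|---|---|---|
| General definition (Section 10) | Ambiguous: refers to a product being administered, but includes marketed products | Arguable |
| Worsening of a pre-existing condition | No | Yes |
| New illness, sign, symptom or laboratory abnormality | Yes | Not literally |
| Events caused by protocol procedures | No | Yes |
| Follow-up for adverse events (Section 8) | No, all groups | Yes |
| Start of recording (Section 10) | No, consent | Yes |
| End of non-serious recording (Section 10; Appendix B note 2) | Yes, last dose | No: there is no last dose |
| Serious-event log (Section 10) | No, consent to discharge | Yes |
| Venous thromboembolism and major bleeding (Appendix C) | No, admission to discharge | Yes |
| Deaths (Section 10; Appendix B) | No, a clinical outcome | Yes |

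Two provisions cannot be applied as written to 50 patients, although Section 8 requires adverse-event follow-up in them. In the AT3 arm, the new-onset entry also omits events between consent and first infusion, although recording starts at consent.

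**3. Direction.** The new-onset entry favours recording in the AT3 arm. The end of the window has no fixed direction. It is undefined in controls, and in the AT3 arm the last dose can fall on any dosing day from Day 1 to Day 9, because Section 8 gives a dose only while AT3 is below 100%.

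**4. Illustrative size.** The documents give no rate for new-onset non-serious events, so the risk is assumed, and is equal in both randomised arms. Expected affected patients per arm are 25 × risk. With x events in the AT3 arm and none in controls, the two-sided Fisher p-value is 2 × C(25,x)/C(50,x).

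- Risk 40%, x = 10: 2 × 3,268,760 / 10,272,278,170 = 0.0006.
- Risk 20%, x = 5: 2 × 53,130 / 2,118,760 = 0.0502.

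Both assume that no control event is captured. If half were captured at 40% risk, the expected table would be 10/25 v 5/25, with Fisher p = 0.22. With full capture it would be 10/25 v 10/25, p = 1.0. The range therefore runs from no distortion to a large one, and the documents do not say where practice would fall.

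**The case against.** The best defence is that the documents plainly intend to record adverse events in everyone. The list says what an adverse event includes, so it is not exhaustive. The separate list of what an adverse event does not include excludes neither undosed patients nor new-onset events. The general definition extends to marketed products, so standard-of-care drugs could satisfy it. Section 8, the consent start and the flowsheet cover every group, and only the dosing row of the flowsheet is restricted to the AT3 arm. Much deterioration in controls would qualify as worsening of an existing illness. Section 9 plans no between-arm adverse-event test, and the stopping rules in Section 12 use absolute events.

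Most of this stands. A reader might infer that new-onset events in controls are not adverse events at all. The documents do not support that, for the reasons just given. A reader might also infer that such events drop out of the serious-event log. That is not supported either: Section 10 logs any serious event from consent to discharge and does not make the three-entry list a condition. A new major bleed is a poor example of a lost event, because Appendix C counts it separately.

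What the defence does not remove is the conflict itself. Section 8 and the flowsheet say who is watched and at which visits, not what counts as an event. The general definition is itself unclear about undosed patients. The third entry specifically admits events outside the treatment period when protocol procedures cause them, which invites staff to read the second entry as limited to dosed patients. No broad reading supplies an end to non-serious recording for a patient without a last dose.

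**Conclusion.** The concern holds as an internal inconsistency, not as an exclusion of control-arm events. The new-onset entry and the close of the non-serious window cannot be applied as written to 50 of 75 patients, including all 25 randomised controls, and they conflict with the follow-up promised to all groups. The exposure is to differential recording of new-onset non-serious events, such as arrhythmia, infection and laboratory abnormalities. Venous thromboembolism, major bleeding, deaths and serious events are protected by separate capture.

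The size of any bias is unknown. The figures of p = 0.0006 and p = 0.050 rest on assumed risks of 40% and 20%, equal in both arms, and on no capture in controls. They mark the worst case and are not a forecast; the second (0.0502) does not meet the protocol's p < 0.05. The change is worth making because it removes a source of asymmetry in an open-label trial at almost no cost.

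**What to change.** 1. In the Section 10 list, replace the study-drug condition on new-onset events with: *after informed consent, whether or not study drug is given*. This matches the existing start of recording.
2. In the general definition in Section 10, state that it applies to all enrolled subjects in all three groups.
3. In the reporting procedures of Section 10 and in Appendix B note 2, replace the last-dose end point for non-serious events with one study day common to all groups. The Day 11 visit is a natural candidate, since the flowsheet already marks adverse events there for everyone.
4. Flag events that occur before randomisation (or before group assignment for patients with AT3 at or above 100%), and list them separately, so that the arms are compared from the same time origin.

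All four are needed: correcting the definition alone would leave controls with no end to non-serious recording. The cost is a few wording edits, one flag on the adverse-event log and somewhat more log entries for undosed patients. No visits are added, because these patients already have the same schedule.

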#### **An AE does not include:**

- The disease or disorder being studied or signs and symptoms associated with the disease or disorder, unless there is worsening of the condition of the disease or disorder
- A pre-existing disease or condition, present at the start of the study, that does not worsen.

### **Procedures for Reporting Adverse Events**

Adverse events may be spontaneously reported, obtained through non-leading questioning, or noted during examination of a subject. Adverse events will be recorded from the signing of informed consent through the last dose of study drug. Serious adverse events will be recorded from the signing of informed consent through hospital discharge.

At each visit, new AEs are recorded sequentially on the **Adverse Event log**. The AE term will note the diagnosis whenever possible, not the individual signs or symptoms (e.g., myocardial infarction will be recorded rather than chest pain, elevated cardiac enzymes, and abnormal ECT). Also recorded are:

- Start and stop date and time
- Whether or not the event is continuing
- Severity (mild, moderate, severe)
  - Mild: usually transient, requiring no special treatment and generally not interfering with usual daily activities
  - Moderate: usually ameliorated by simple therapeutic maneuvers and impairs usual activities
  - Severe: requires vigorous therapeutic intervention and interrupts usual activities. Hospitalization may or may not be required.

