**6) Study Timelines\***

- a. Subject participation will be approximately 11 days from the time of consent to the last blood draw. After the last blood draw, only routine clinical data will be followed and captured from the medical record to outcomes.
- b. Enrollment of 75 subject will be over the course of 12 to 18 months.
- c. The primary analyses should be completed within 24 months from the time of study initiation.

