### Dosing Rationale-

In those COVID(+) patients with an endogenous AT3 activity level <100% and at the discretion of the attending physician, Day 1 infusion of AT3 will be at a dose to be adjusted based on initial body weight up to 100 kg maximum and to a set target plasma activity level of 120% according to the following formula:

$$= \frac{(120\% - \text{baseline AT3}\%)}{1.4} \times \text{body weight (kg)}$$

Based on an example of an 85kg patient with a baseline AT activity level of 90%,

- The dose would be 1,821 units on a dosing schedule of Day 1, 3, 5, 7 & 9
- For a total of approximately 9100 units
- Each Thrombate III vial contains 500 units each reconstituted with 10 mL of Sterile Water for Injection, USP, the final concentration is approximately 50 units per mL.
- Requiring 4 vials per dose or 20 vials per patient

Each 85kg patient will receive ~9100 IU's over 5 doses requiring 20 vials

- (10% overage to account for any dose adjustments needed)
- therefore each patient would require 10,000 IU's
- for a total of 250,000 IU's or 500 vials for the study.

AT3 will be drawn every other day, pre-dose, for monitoring, and verification of 120% target plasma activity level. Dosing schedule will be as follows: Day 1, 3, 5, 7 & 9 a dose will be given if AT3 activity level remains less than 100% on those days, otherwise no dose will be given. Days refer to a 24 hour period.

Data to be collected from the medical record according to the Study Flowsheet (Appendix B) will include:

- a. Demographics: age, comorbidities, medical history, concomitant meds, vital signs, height and weight,
- b. ISTH DIC score and a Sofa Score,
- c. Laboratory values:
  - a. Platelets, PT, INR, PTT, D-Dimer, Fibrinogen, AT3 level, Anti-Xa,
- d. Outcomes:
  - a. Length of Stay, Mortality, change in PF ratio, Vent/ECMO days, # and severity VTE's, # and severity of bleeding events

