**Appendix B**

Study Subject Flowsheet	Enrollment - Day 1*	Days 3, 5, 7 & 9	Day 11	On Discharge
Informed Consent	x			
Entry Criteria	x			
Demographics	x			
Medical and Surgical History	x			
Prior & Concomitant Medications	x	x	x	x
Vital Sign Measurements	x	x	x	
ISTH DIC Score	x	x	x	
SOFA Score	x		x	
Blood Draw	x	x	x	
Urine or Serum Pregnancy Test if applicable	x			
Platelet	x	x	x	
PT, INR	x	x	x	
PTT	x	x	x	
Hemoglobin and Hematocrit	x	x	x	
Fibrinogen	x	x	x	
D-Dimer	x	x	x	
AT3 Level	x	x	x	
Anti-Xa	x	x	x	
Dosing if randomized to group with AT3 Infusion 	x 	x 		
Adverse Events 	x	x	x	x 
Hospital LOS				x
Mortality				x
PF ratio change				x
Days on Ventilator				x
Days on ECMO				x
VTE's				x
Bleeding Events				x

\*: Day refers to a 24 hour period.

x: To be completed

1: Only if randomized to AT3 Infusion and AT3 level is at specified level

2: Only Serious Adverse Events will be captured from last dose to hospital discharge.

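### Non-serious adverse event recording ends at the last dose, which 50 of 75 patients never have, and conflicts with visit-based recording to Day 11; VTE and major bleeding are also counted from admission, not from randomisation.

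*Combined protocol and SAP*

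**What the plan says.** **Adverse events.** Section 10 (Procedures for Reporting Adverse Events) sets the window for non-serious events: "Adverse events will be recorded from the signing of informed consent through the last dose of study drug". Serious events run from consent to hospital discharge. Appendix B, footnote 2, agrees: "Only Serious Adverse Events will be captured from last dose to hospital discharge".

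Other text describes a window tied to visits:

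- Section 8, of all three groups: "They will all be followed up for laboratory blood tests, study endpoints and adverse events".
- Section 10, same heading as the cut-off: "At each visit, new AEs are recorded sequentially". Section 8 puts the visits on Days 1, 3, 5, 7, 9 and 11.
- Section 6: "Subject participation will be approximately 11 days from the time of consent to the last blood draw".
- Appendix B marks the adverse event row at Day 11. The discharge cell carries the footnote marker; the Day 11 cell does not.

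Section 4 defines group a (AT3 at or above 100%, standard of care), group b ("25 patients with endogenous AT3 <100% who receive standard of care only") and group c (AT3 below 100%, standard of care plus AT3), with 25 patients each. Doses in group c are scheduled for Days 1, 3, 5, 7 and 9, and the Dosing Rationale adds: "a dose will be given if AT3 activity level remains less than 100% on those days, otherwise no dose will be given". One of the three items defining an AE in Section 10 covers conditions "detected or diagnosed after study drug administration".

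**VTE and major bleeding.** Appendix C, items i and j, count both from admission to discharge, whereas items a to c, g and h of the same list measure change from baseline. Section 5 recruits patients who are already inpatients and sets no limit on time since admission. Appendix B collects both outcomes once, at discharge.

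**The concern.** A window that closes at the last dose cannot be applied to patients who are never dosed, and the plan gives them no substitute end date. That leaves the randomised control arm without a defined end to non-serious AE recording under the stated rule. In group c the end depends on each patient's AT3 course, so the observation period depends on response to treatment. A patient who misses the Day 3 dose may be dosed again on Day 5, so the last dose may be identifiable only in retrospect.

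The plan does not say whether the last-dose rule or the visit schedule governs. The trial is open label, so staff know who is on AT3 and could apply the dose-based rule to that arm alone. Group c would then be watched for less time than group b, and AT3 would look better tolerated than it is. Section 13 reports no serious reactions in the earlier trials of the product (29 reactions in 9 of 33 subjects), so the non-serious log is the likeliest place for a tolerability difference to appear.

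The starting point for VTE and bleeding is a separate and smaller matter. On the plain reading, events before randomisation are counted, and treatment cannot have affected those.

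**Working it through.** **1. Patients without a last dose.** From Section 4, 25 + 25 + 25 = 75, and groups a and b give 25 + 25 = 50. The drug supply in Section 8 agrees: 250,000 IU at 10,000 IU per patient is 25 treated patients.

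**2. Length of the window in group c.** A last dose on Day 1, 3, 5, 7 or 9 leaves 10, 8, 6, 4 or 2 days to Day 11 without non-serious recording. The observed share of the 11 days is 1/11 = 9% at the shortest and 9/11 = 82% at the longest.

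**3. Three readings.**

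- Visits to Day 11 govern all groups: equal windows, no effect.
- Last dose governs all groups: the window is undefined for 50 patients.
- Mixed (group c stops at last dose, controls go to Day 11): unequal windows.

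**4. Size on the mixed reading.** Assume the same constant daily risk in both arms, no early discharge, and a proportion p of controls with at least one AE by Day 11. With the last dose on Day L, group c shows 1 − (1 − p)^(L/11). The documents give no AE rate, so p is assumed. For p = 0.50, controls show 12.5 of 25 patients:

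| All last doses on | Group c proportion | Group c, of 25 | Shortfall |
|---|---|---|---|
| Day 9 | 1 − 0.5^(9/11) = 0.433 | 10.82 | 1.7 |
| Day 5 | 1 − 0.5^(5/11) = 0.270 | 6.76 | 5.7 |
| Day 1 | 1 − 0.5^(1/11) = 0.061 | 1.53 | 11.0 |

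With all last doses on Day 9, p = 0.30 or 0.80 gives a shortfall of 1.2 or 1.7 patients. The Day 1 row is an extreme in which no patient is dosed again; a real trial would mix these cases.

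**5. VTE counted from admission.** Section 2 cites deep vein thrombosis in 6 of 40 patients (15%), so group b would have 25 × 6/40 = 3.75 events. That is DVT alone; the same series also reports thromboembolism (5%) and catheter-related thrombosis (30%). Assume a true relative risk of 0.50 after randomisation, and let f be the share of control events that precede it (assumed). The apparent ratio is f + 0.50 × (1 − f).

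| f | b, c from admission | Ratio | Difference | b, c from randomisation | Ratio | Difference |
|---|---|---|---|---|---|---|
| 0.2 | 3.75, 2.25 | 0.60 | 1.50 | 3.00, 1.50 | 0.50 | 1.50 |
| 0.5 | 3.75, 2.81 | 0.75 | 0.94 | 1.88, 0.94 | 0.50 | 0.94 |

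Earlier events add the same expected number to both arms (0.75 or 1.88), so they cancel from the difference and dilute only the ratio. Exact power of a two-sided Fisher test at 0.05, 25 against 25, is 3.5% and 2.4% counting from admission, and 2.4% and 0.4% counting from randomisation. At this size the issue is descriptive.

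**The case against.** **The visit schedule already supplies a workable window.** Section 8 follows everyone for adverse events, new ones are logged at each visit, and the Day 11 cell is marked without a footnote. On that reading the windows are equal. This is a fair reading, and a reader who infers that controls go without AE follow-up, or that AT3 events will certainly be under-recorded, goes further than the documents. The mixed rule is one that the text permits but nowhere states. What stands is that the explicit sentence in Section 10 and footnote 2 both say something else, and nothing settles which prevails.

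**Little safety information is lost.** Serious events run to discharge, VTE and bleeding are collected separately, and unresolved events are followed to discharge or stabilisation. Section 10 says common disease-related abnormalities do not necessarily count as AEs. The reactions in the cited trials occurred during infusions and would be logged on any reading. All this stands. The loss is confined to new, non-serious events after the final dose; following unresolved events does not capture new ones. Section 9 plans no AE test.

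**Counting from admission may be harmless.** Section 8 speaks of a SOFA score at admission that Appendix B places at enrolment Day 1, so admission may mean Day 1, with no effect. Exclusions h and i (ongoing massive or unexplained bleeding; history of a bleeding or clotting disorder) may also remove some patients with earlier bleeding. Both points stand, but the term is undefined and the plain meaning for inpatients is hospital admission. A reader might infer that this count shrinks the b versus c difference in events. It does not: for any given f the expected difference is the same with either starting point.

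**Conclusion.** The concern holds as an unresolved conflict between a dose-based and a visit-based window for non-serious adverse events. It should be corrected, but it does not threaten the primary analysis. The size runs from nothing, if Day 11 governs all groups, to a shortfall of about 1.7, 5.7 or 11.0 of 25 patients in group c on the mixed reading with all last doses on Day 9, 5 or 1. Those figures rest on equal constant risk, 50% of controls affected by Day 11 and no early discharge, none of which comes from the documents. The damage would be to the pilot's description of tolerability, in the direction that favours AT3.

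The starting point for VTE and major bleeding is a secondary point. Between groups b and c, events before randomisation add noise and dilute a ratio (an assumed 0.50 appears as 0.60 or 0.75 if 20% or 50% of control events come earlier), while the expected difference in counts is unchanged. Group a is not randomised, so earlier events need not balance there and may bias comparisons with it.

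**What to change.** **Section 10 and Appendix B, footnote 2.** Record all adverse events from consent through the Day 11 visit, or discharge if earlier, in all three groups regardless of doses given. Keep serious events to hospital discharge. Amend footnote 2 to match.

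**Section 10, AE definition.** Change "detected or diagnosed after study drug administration" so that it refers to the time after enrolment and applies to patients who receive no study drug.

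**Appendix C, items i and j.** Count new events from randomisation (enrolment Day 1 for group a) to hospital discharge, and record earlier events as baseline history.

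**Cost.** This is a wording amendment: visits to Day 11, Day 1 medical history and chart review at discharge are already planned. It brings slightly more AE logging and, on the plain reading of admission, fewer counted VTE and bleeding events.
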